We anticipate low, but potentially important rates of survey non-response to all or part of the 6- and 12-month surveys. We will use the evidence-based recruitment strategies described above (incentives, reminders, mixed mode survey administration) to minimize non-response. A common practice in smoking cessation research is to treat non-respondents at follow-up as continuing smokers (i.e., intent to treat). This practice is perceived to be a conservative approach but does not, in fact, produce valid estimates of quit rates.³³ We will use multiple imputations to fully use available baseline information and partial later surveys. We will use a propensity-based multiple imputation method similar to that discussed by Little³⁴ using separate imputation procedures within each study group and design stratum combination. Within a given combination, we will estimate the propensity for responding to cotinine validated abstinence for each individual from a logistic regression model for survey response using the characteristics measured at baseline as explanatory measures. Within a combination of intervention and design strata, we will further stratify the sample according to the values for these estimated propensities. Within a propensity substratum, we will impute a value for the outcome measure for each non-respondent by randomly sampling an outcome value from the respondent values in the substratum. Multiple completed datasets will be created and the point estimates and the estimated standard error from each dataset will be combined to arrive at a single point estimate (using the specific method discussed below), its estimated standard error, and the associated confidence interval or significance test. This approach assumes that missing outcome data due to non-response is missing at random.

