To assess the impact of non-ignorable survey non-response, or missing not at random non-response, we will implement pattern-mixture analyses. Using content expertise and the observed missing data patterns, we will develop these pattern-mixture models. The nature of these models is difficult to specify in advance of observing the different patterns but we will posit distributions for the missing data. For each set of posited distributions and the observed data, we will calculate revised estimates for the relevant intervention effects. One potential model would be to use the propensity stratum derived in the analysis described above and, within each stratum build a distribution for the outcome of interest by shifting the observed distribution among the responders. Content expertise and empirical results will be used to determine the form and magnitude of shift. These distributions would then be used to impute values for the non-responders to cotinine validation in the imputation process described immediately above. Variations of this approach and other approaches will be used to assess the sensitivity of the analyses above to non-ignorable non-response.

We will be enrolling patients after they complete the baseline survey, which maximizes our internal validity; thus we will have baseline data on all participants. The methods above for imputing missing data address the issue of non-response to all or part of either the 6-month or 12-month survey and cotinine validation. We will have limited data available on those who do not respond to the baseline survey, but we will use what data we have to compare initial responders to non-responders, in order to address external validity.

Specific aim analysis

The data will first be summarized numerically using descriptive statistics and frequency distributions examined for validity. Comparison of the baseline demographic and tobacco use characteristics between the two treatment groups will be performed using chi-square tests for categorical data and t-tests or nonparametric tests for ordinal or continuous data.

Aim 1: Compare the reach and efficacy of a proactive outreach telephone-based tobacco cessation (PRO) program for patients seen in mental health to usual care (UC) advice and referral to local VA and community tobacco cessation resources.

H1: Compared to the control group, the proactive intervention will increase the smoking abstinence rate at 12 month follow up.

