H2: We hypothesize that mental distress and active substance abuse are the strongest baseline predictors of treatment uptake and long-term abstinence in a mental health population.

Method: We will use a generalized linear mixed model approach³⁶ to determine smoking outcomes at 6 and 12 months. Following the recommended best practices in longitudinal data analysis,³⁷ we will use a two-level hierarchical linear model to fit the data. The outcome variable of interest will be the dichotomous cotinine-validated smoking abstinence data. Therefore, a logit model is appropriate at Level 1, where individual outcomes will be fitted for each subject using time as the primary covariate. The parameter estimates from these individual functions will then be entered as dependent variables in Level 2 in which treatment group (PRO vs. UC) is the covariate. This longitudinal analytic approach will help understand to what extent treatment effects differ between 6 and 12 months and whether they show a delayed effect (either increasing or decreasing over time). This will allow us to determine a treatment main effect as well as a treatment by time interaction. Baseline covariates will be included at the patient level (age, sex, race/ethnicity, nicotine dependence, motivation, self-efficacy, mental distress, and current substance use). Inclusion of covariates typically reduces residual errors and thus boosts statistical power as well as allows us to determine factors that affect abstinence to better target intervention design and content.

Power calculations

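### The response-propensity hot deck for missing abstinence does not carry the covariate or between-visit information that Aim 2 estimates, so Aim 2 associations are generally pulled toward zero, by an amount the plan does not let us fix

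*Combined protocol and SAP*

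**What the plan says.** All references are to the combined protocol and SAP. Section 6.0, Missing Data, sets out one imputation method:

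- It opens with an aim: "We will use multiple imputations to fully use available baseline information and partial later surveys".
- The work is done "using separate imputation procedures within each study group and design stratum combination", that is, by arm and site.
- A response score is estimated "from a logistic regression model for survey response using the characteristics measured at baseline as explanatory measures", and each cell is split into bands of that score.
- Within a band, "we will impute a value for the outcome measure for each non-respondent by randomly sampling an outcome value from the respondent values in the substratum".
- The methods are said to "address the issue of non-response to all or part of either the 6-month or 12-month survey and cotinine validation".
- The completed datasets are analysed by the methods given later in the section and the results are pooled.

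On the amount of missing data it says only: "We anticipate low, but potentially important rates of survey non-response to all or part of the 6- and 12-month surveys".

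The Aim 2 method, later in Section 6.0, is a two-level logit model for validated abstinence at 6 and 12 months. It states: "Baseline covariates will be included at the patient level (age, sex, race/ethnicity, nicotine dependence, motivation, self-efficacy, mental distress, and current substance use". It does not mention missing outcomes. Dependence and motivation are collected in the baseline survey (5.7.1). Demographics, self-efficacy, distress, alcohol and drug use are listed under the 2-week survey (5.7.2).

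**The concern.** A hot deck preserves only those relations on which donors and recipients are matched. Here they are matched on arm, site and likelihood of responding. Within a band, a filled-in abstinence value is unrelated to the recipient's distress, substance use or self-efficacy, and to whether the same person was abstinent at the other visit. The stated intent to draw on partial later surveys is not carried into any step.

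Aim 2 estimates these very relations. If its model is fitted to the completed data, real associations are diluted by records in which the association is weak or absent, and the correlation between visits is diluted too. H2 is exposed in its abstinence part. Section 6.0 words H2 as distress and substance abuse being the strongest predictors, so unequal dilution across covariates could also change the ordering that H2 examines.

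**Working it through.** **The plan's own figure.** The only relevant stated figure is power for Aim 1. Population quit rate under intervention: 0.20 × 16% + 0.80 × 4% = 6.4%. With 1,920 per arm and two-sided alpha 0.05, the pooled standard error is √(2 × 0.052 × 0.948 / 1920) = 0.00717 and the unpooled one √((0.04 × 0.96 + 0.064 × 0.936) / 1920) = 0.00716. Power = Φ((0.024 − 1.96 × 0.00717) / 0.00716) = Φ(1.39) = 0.918, against the stated 90%. This supports the 4% and 6% rates used below. The plan has no figure for Aim 2 or for missing data, so every missing fraction here is an assumption.

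**First-order result.** Let p(x) be the abstinence probability at covariate value x, p̄ its average in the band, β the log odds ratio and m the missing fraction. If x is unrelated to response within the band, the completed data have probability (1 − m)p(x) + m·p̄. The logit slope near the mean is then about (1 − m)β, a loss of about m. If x strongly drives response and is in the score, people in one band have similar x, p̄ is close to p(x), and the loss shrinks toward zero.

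**Single-outcome logit, n = 3,840.** About 6% abstinent; eight arm-by-site cells; score quintiles; 100 trials with five imputations each. Log odds ratio for distress per SD:

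| Missing | Full data | Observed only | Hot deck | Kept | 1 − m |
|---|---|---|---|---|---|
| 15% | −0.502 | −0.498 | −0.413 | 82% | 85% |
| 25% | −0.516 | −0.516 | −0.369 | 72% | 75% |
| 35% | −0.516 | −0.517 | −0.315 | 61% | 65% |

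At 25% missing, an odds ratio of exp(−0.516) = 0.60 becomes exp(−0.369) = 0.69. With distress added to the response model, 84%, 76% and 62% is kept. The arm log odds ratio stays at 0.97–1.01 of its full-data value.

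**Two visits, large sample.** About 4% and 6% abstinent by arm; log odds ratio −0.5 per distress level and for substance use; random-intercept SD 2.0; score quintiles within arm, site omitted; separate donor draw at each visit; response unrelated to the two covariates. Loss of slope for distress and substance use:

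| Missing | Pooled logit | Random-intercept logit | 6-to-12-month correlation |
|---|---|---|---|
| none | – | – | 0.24 |
| 10% | 9–11% | 13–15% | 0.20 |
| 20% | 19–20% | 26–27% | 0.17 |
| 30% | 29–32% | 37–40% | 0.14 |
| 40% | 39–41% | 48–49% | 0.12 |

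The random-intercept loss is larger because the between-visit correlation falls and takes the random-intercept SD with it (2.0 to about 1.65 at 20% missing).

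**When distress drives response (20% missing).**

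- Distress in the score, with log odds of response −0.3, −0.7 and −1.5 per level: the distress loss is 14%, 8% and about 0% (pooled), and 21%, 15% and 7% (random intercept).
- In the −0.7 case substance use still loses 18% (pooled) against 8% for distress, so dilution can differ between covariates.
- Distress left out of the score (−0.3 and −0.7): 21–22% (pooled) and 28–30% (random intercept).

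**Against sampling error.** n = 3,840, about 5% abstinent, distress outside the score, standard error about 0.08:

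| Missing | Log odds ratio | Shift | Shift / 0.08 |
|---|---|---|---|
| 5% | −0.56 to −0.54 | 0.02 | 0.25 |
| 10% | −0.58 to −0.52 | 0.06 | 0.75 |
| 20% | −0.58 to −0.46 | 0.12 | 1.5 |
| 30% | −0.55 to −0.38 | 0.17 | 2.1 |

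**Check of the remedy.** In the two-visit set-up, matching donors on arm, the covariates and the other visit brings the loss to within ±2.5% at 10–40% missing, and the random-intercept SD stays at about 2.0.

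**The case against.** Several objections have force.

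- **Aim 2 may not use the imputed values.** Its method paragraph never mentions imputation, a mixed model can be fitted to observed visits, and the reference to 6-month non-response could concern the 6-month secondary outcomes in 5.8. This stands as a gap in the text. But one imputation method is given, its results feed the analyses that follow, and no exception is made for Aim 2.
- **The bands do contain covariates.** A reader might infer that none of the Aim 2 covariates enter. Dependence and motivation come from the baseline survey, so they do. For the 2-week measures the text is ambiguous: the Aim 2 paragraph calls them baseline covariates, and 5.7.2 speaks of baseline comorbidity, while Missing Data links having baseline data on everyone to the baseline survey.
- **Other-visit data are intended.** True, and the method is described as similar to a cited procedure for gaps in longitudinal data, which is not available here. The written steps still do not use them.
- **Non-response is expected to be low.** At 5–10% the bias would hardly be noticed. The word low, however, describes survey non-response; no rate is given for saliva return.
- **Treatment by time.** A reader might infer that this term is distorted. Imputing within arm at each visit keeps the arm-by-visit rates, and the marginal interaction hardly moved at 5–30% missing (−0.22 and −0.22; −0.28 and −0.29). No figure supports that inference.

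The planned pattern-mixture analyses do not help: they revise intervention effects, and the one model described reuses the same bands.

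**Conclusion.** The concern holds in a limited form. If the Aim 2 model is fitted to outcomes completed by this hot deck, associations between covariates and abstinence are generally pulled toward zero and the 6-to-12-month correlation is reduced. Distress, substance use and self-efficacy are most exposed if the 2-week measures are left out of the response model.

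A fixed rule that the loss equals the missing fraction is not supported. At 20% missing it ran from about 0% to 30%, depending on the analysis model and on what drives response. Its absolute size cannot be settled, because the plan states no missing rate and the 5–40% range is assumed.

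Nor do the documents support reading this as a fault in all of H2 or in the primary result. Treatment uptake has its own regression. The Aim 1 arm contrast is largely protected by imputing within arm: the pooled arm effect changed by about 2% at most in the two-visit simulation, although the arm coefficient in a random-intercept logit fell by 2–13%. The general effect on Aim 2 is weaker associations and lost power, not invented ones. This should be fixed before analysis, but it is a secondary-aim matter.

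**What to change.** Keep the hot deck for Aim 1. Add one SAP paragraph for Aim 2 that does the following:

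1. States which data the model uses: either maximum likelihood on all observed visits, or imputation of both visits' outcomes from a model (or donor match) with arm, site, every Aim 2 covariate and the other visit's smoking data.
2. Separates self-report from cotinine. Under 5.7.4 only self-reported abstainers are tested, so putting same-visit self-report into a logistic imputation model causes separation at event rates of 4–6%. Where self-report is observed, set validated abstinence to no for self-reported smokers, and impute cotinine status only among self-reported abstainers without a valid sample. This step is needed under the likelihood option too, because samples can be missing only among people who report abstinence. Say also how abstinent people using nicotine replacement, who are not tested, are classified.
3. States that the 2-week measures are included as predictors, and imputes them when missing. Otherwise the likelihood option drops people without a 2-week survey.

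No new data are needed. The cost is one paragraph, some programming and, if the imputation route is chosen, a second imputation model to document.

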5.7.4 Saliva Sample - Validation of self-reported abstinence

Self-reported smoking abstinence can be verified by assays of cotinine, the principal metabolite of nicotine. Patients with cotinine levels > 15ng/ml will be classified as current smokers.³² Sample collection will be conducted by mail. Patients will be eligible for verification if they report 7-day abstinence from cigarettes, other tobacco products, e-cigarettes and nicotine replacement therapy (NRT). A research assistant will send a saliva collection kit, collection instructions (Appendix D), a collection date sheet (Appendix E), and a postage-paid return envelope on the day of telephone survey with a postage paid return envelope. Subjects will receive a reminder call 5 and 8 days later. If they do not respond, another kit will be sent at 2 weeks, followed by two more reminder calls. We will mail a \$25 payment to participants who return a saliva sample.

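### The listed imputation steps for the primary outcome omit the 12-month self-report and do not define a respondent, so no single donor pool suits both missing saliva and missing surveys

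*Combined protocol and SAP*

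**What the plan says.** The primary outcome is reached in two steps: a 12-month survey, then a mailed saliva test for some respondents. Section 5.7.4 sets who is tested: "Patients will be eligible for verification if they report 7-day abstinence from cigarettes, other tobacco products, e-cigarettes and nicotine replacement therapy (NRT").

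Section 6.0, Missing Data, gives one imputation procedure, run separately by arm and design stratum (site). It states an aim: "We will use multiple imputations to fully use available baseline information and partial later surveys". The first listed step is to "estimate the propensity for responding to cotinine validated abstinence for each individual from a logistic regression model for survey response". The inputs to that model are limited to baseline data, since it is fitted "using the characteristics measured at baseline as explanatory measures". The next steps are to form substrata of that propensity and to "impute a value for the outcome measure for each non-respondent by randomly sampling an outcome value from the respondent values in the substratum". The stated assumption is: "This approach assumes that missing outcome data due to non-response is missing at random". The same paragraph rejects counting non-respondents as smokers, because that practice "does not, in fact, produce valid estimates of quit rates".

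The subsection then describes pattern-mixture sensitivity analyses, with one example: "These distributions would then be used to impute values for the non-responders to cotinine validation in the imputation process described immediately above". Its last paragraph says that the imputation methods cover missing survey data and missing cotinine validation alike. The Aim 1 analysis works on the log odds of 12-month abstinence.

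**The concern.** Someone who completes the 12-month survey and reports smoking has a known outcome. A survey respondent whose cotinine result is missing is therefore a self-reported abstainer. That self-report is the strongest available predictor of the missing value, yet the listed steps condition only on arm, site and a baseline propensity. Given those variables alone, missing saliva still depends on self-reported abstinence, so the missing-at-random assumption cannot hold for it.

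The propensity sentence also names two response events, cotinine and survey, and donors are called respondents without definition. Two readings are possible:

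- **Smokers as donors.** Everyone with a determined outcome is a donor. This is the more natural reading, because the modelled event is survey response. Abstainers without saliva then draw from a pool made up almost entirely of smokers.
- **Assay-only donors.** Only people with a cotinine result are donors. Missing saliva is then filled sensibly if non-returners resemble returners, but survey non-respondents draw from a pool made up mostly of confirmed abstainers.

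At stake are the reported quit rates, the absolute difference, power and, in some circumstances, the odds ratio and type I error of the primary comparison.

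**Working it through.** **Inputs from section 6.0, Power calculations:** 1,920 per arm, two-sided 0.05, 4.0% vs 6.4%. The 6.4% reproduces: 0.2 × 16% + 0.8 × 4% = 6.4%. The normal-approximation power is 91.8% (90.6% with continuity correction), against 90% stated. The odds ratio is (0.064/0.936)/(0.04/0.96) = 1.64.

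**Assumed, because the plan gives no figure:** confirmation among tested abstainers c = 80%; kit return r = 50-90%; survey response q = 90-95% for the assay-only reading, complete surveys otherwise. With p the true validated rate, self-reported abstinence is p/c: 5% in control and 8% in PRO.

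**Smokers as donors.** The donor-pool mean, which is also the probability imputed to an abstainer without saliva and the estimated rate, is p·r / [1 − (p/c)(1 − r)]. At r = 0.7:

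- control 0.028/(1 − 0.05 × 0.3) = 2.84%
- PRO 0.0448/(1 − 0.08 × 0.3) = 4.59%

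| Kit return, both arms | As listed | Missing = smoking (p·r) | Difference as listed, points | OR as listed | Power as listed vs two-stage |
|---|---|---|---|---|---|
| 50% | 2.05% vs 3.33% | 2.00% vs 3.20% | 1.28 | 1.65 | 0.67 vs 0.86 |
| 70% | 2.84% vs 4.59% | 2.80% vs 4.48% | 1.75 | 1.64 | 0.82 vs 0.90 |
| 90% | 3.62% vs 5.81% | 3.60% vs 5.76% | 2.19 | 1.64 | 0.89 vs 0.91 |

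Power is simulated: 12,000 runs, 4 sites, 5 strata, 20 imputations, and a site-stratified Mantel-Haenszel log odds ratio combined by Rubin's rules, standing in for exact logistic regression. Full-data power in this set-up is 0.92. Strata that predict abstinence hardly help: with a nine-fold spread and 70% return, the rates are 2.86% vs 4.62% and power is 0.82 vs 0.89.

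**No true effect (4% in both arms), return 70% in one arm and 50% in the other.** The estimates are 2.84% and 2.05%, OR 0.72. The pooled standard error is √(2 × 0.02447 × 0.97553/1920) = 0.00499, so the expected z is 0.00791/0.00499 = 1.59, and rejection is about P(Z > 1.96 − 1.59), or 35%. Simulation gives 33-35%, and about 5-6% with two-stage imputation.

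**Equal return does not always protect the odds ratio.** Take no true effect, 70% return and 68% overall confirmation in both arms, with non-returners confirming at 60% in one arm and 40% in the other. Self-report is 0.04/0.68 = 5.88%. Returners then confirm at (0.68 − 0.3 × 0.6)/0.7 = 71.4% and (0.68 − 0.3 × 0.4)/0.7 = 80%. As listed, the rates are 2.99% vs 3.35%, OR 1.12. Two-stage gives 4.20% vs 4.71%, OR 1.13.

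**Assay-only donors.** The estimated rate is q·p + (1 − q)·c.

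- q = 0.95: 0.038 + 0.040 = 7.8% vs 0.0608 + 0.040 = 10.1%, OR 1.33
- q = 0.90: 0.036 + 0.080 = 11.6% vs 0.0576 + 0.080 = 13.8%, OR 1.22

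Survey response is equal by arm here, and the odds ratio still falls.

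**Both kinds missing together** (assumed c = 0.7, r = 0.6, q = 0.8; simulation): smokers as donors 2.5% vs 4.0%; assay-only 17.2% vs 19.0%; two-stage 4.0% vs 6.35%.

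**The case against.** The strongest reply is that this is under-specification, not error. The plan states the aim of using partial later surveys, and a completed survey without saliva is a natural example. It also calls its method only similar to a cited one. A reader might infer that the authors have chosen to ignore the self-report. The documents do not support that: they show that no listed step uses it. That is still a gap in the primary analysis. Two programmers following the same text could report control abstinence near 2.8% (70% kit return, complete surveys) or near 11.6% (90% survey response).

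A reader might also infer that the trial's odds ratio will be biased or its type I error inflated. That is not shown. With smokers as donors, and with return and confirmation alike in both arms, the odds ratio is essentially unchanged and the loss is in rates, absolute difference and power. At 90% return the power loss is about 2 points, and section 5.7.4 provides reminder calls, a second kit and a payment. The opposite inference, that equal return is enough to protect the odds ratio, also fails, as the 60%/40% case shows.

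The pattern-mixture analyses do not answer the point. They are open-ended sensitivity analyses, and the example given reuses the same propensity strata.

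Finally, the two-stage method is not better in every case. It assumes that non-returners confirm like returners within arm, which the data cannot check. This objection stands and shapes the fix.

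**Conclusion.** The point holds for the steps as listed and should be fixed. It follows from sections 5.7.4 and 6.0 alone that a single baseline-stratified draw cannot suit both kinds of missing data. Smokers as donors is harmless only with complete kit return, and assay-only donors only with complete survey response.

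The sizes rest on assumed return, confirmation and survey response. Under smokers as donors with equal 50-90% return and 80% confirmation, the planned 2.4-point difference shrinks to 1.28-2.19 points. The odds ratio is preserved, in general, only if kit return and confirmation among non-returners (relative to returners) are both alike in the two arms. Under assay-only donors the odds ratio is pulled towards 1 even with equal response. Confidence is high in the gap and lower in the amount of harm, because the documents give no evidence on kit return or confirmation in either arm.

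**What to change.** Rewrite the listed steps of section 6.0, Missing Data, as two stages.

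- **Before stage 1.** Define respondent and donor for each stage. Code 12-month self-reported smokers as non-abstinent.
- **Stage 1.** For survey non-respondents, impute 12-month self-report, including whether the person would be eligible for saliva, from survey respondents within arm and site, using the baseline propensity and 6-month smoking status.
- **Stage 2.** For observed or imputed saliva-eligible abstainers with no result, draw the cotinine result only from assayed self-reported abstainers in the same arm, pooling sites. State that this departs from the plan's within-site rule, and why: at 70% return the control arm holds about 1,920 × 5% × 0.7 = 67 such donors, or 67/20 ≈ 3.4 per cell with 4 sites and 5 strata (assumed).
- **Not sent a kit.** Exclude from stage 2 the abstainers not sent a kit because of NRT or e-cigarette use, and state separately how the primary outcome classifies them.
- **Sensitivity.** Add to the pattern-mixture analyses a prespecified version with lower confirmation among non-returners, varied separately by arm over a wide range (for example 60%, 40%, 20%). Do not fix a break-even value, since it depends on the assumed set-up.
- **Reporting.** Report kit return and saliva eligibility by arm.

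The cost is SAP wording and a little programming, with no new data. The downside is that if non-returners confirm much less often and return differs by arm, the fix can be more biased than the listed steps. With no true effect, 68% overall confirmation, 40% among non-returners, and return of 70% in control and 50% in PRO, returners confirm at 80% and 96%. The fix then gives 5.88% × 0.80 = 4.71% vs 5.88% × 0.96 = 5.65%, OR 1.21 in favour of PRO. The listed steps give 3.35% vs 2.91%, OR 0.86. The sensitivity analysis is therefore part of the fix.
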